2. BACKGROUND

2.1 Advanced Head and Neck Cancer

More than half of patients with head and neck squamous cell carcinoma (HNSCC) have locoregionally advanced cancer and approximately 10% have metastatic disease at the time of their initial diagnosis. Patients with resectable disease who receive adjuvant chemoradiation treatment (CRT) following surgery have a 5-year recurrence rate of 20%. Although some patients with recurrent disease can be salvaged with surgery or radiation therapy, the majority are incurable and are treated palliatively with systemic therapy. Patients with recurrent and/or metastatic (R/M) HNSCC receiving first- line chemotherapy for recurrent disease have a median overall survival (OS) of ~7 months. The prognosis for patients with R/M HNSCC when first-line chemotherapy fails for recurrent disease is dismal, with median OS of < 6 months [1].

The most common non-targeted, first-line treatment approach for R/M HNSCC in patients who are not candidates for surgery or radiation treatment is a platinum-containing agent (cisplatin, carboplatin) combined with either 5-fluorouracil (5-FU) or taxane (paclitaxel, docetaxel). Response rates and OS in HNSCC following platinum-based dual agent chemotherapy are low, i.e., response rates are about 20-30% and median OS between 6.5 and 8.0 months, across several studies [2]. Addition of cetuximab improves response marginally; in a Phase 3 study of R/M HNSCC patients receiving platinum-based chemotherapy and 5-FU, the median OS was prolonged from 7.4 months with chemotherapy alone to 10.1 months with addition of cetuximab. Median progression free survival (PFS) was also increased from 3.3 months to 5.6 months [3]. It should be noted that subjects in the study were in good general condition and had good organ function. However, not all patients are able to tolerate the intensive triple-drug chemotherapy regimen and are offered alternative therapies, e.g., dual therapy with platinum + taxane followed by monotherapy with cetuximab [4].

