Subjects will be monitored for clinical safety events and changes in laboratory parameters throughout the study period. Subjects who experience a CR before the next cycle will not receive treatment but will continue to be followed during the study period. Subjects whose tumors achieve a CR but then recur during the study period may resume treatment with Ad/PNP-F-araAMP up to the maximum allowed 5 total cycles.

No formal follow-up visits are planned following the end of the study period (Day 56 of the last treatment cycle). However, the Investigational New Drug (IND) Sponsor may request follow-up information from the investigator on tumor status in subjects who have stable disease (SD), PR, or CR at completion of their study participation.

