12.6 Assessment of Efficacy Measures

Response (CR, PR, SD, PD) is based on the Response Evaluation Criteria in Solid Tumors (RECIST<http://www.ctep.info.nih.gov> v1.1) [6] and defined in Sections 9.3.4 and 10.

Efficacy assessments include:

- ORR is defined as the percentage of patients with a BOR of CR or PR. BOR is the best response achieved during the 5 cycles of treatment, as per Section 9.3.4 for injected tumors and overall as determined by RECIST v.1.1.
- Durable response rate is defined as a BOR of CR or PR as per Section 9.3.4 for injected tumors and overall as determined by RECIST v. 1.1 persisting for at least 4 weeks.
- TTR is defined as time from first intratumoral injection to date of first response value of CR or PR for injected tumors as per Section 9.3.4 and overall as determined by RECIST v.1.1.
- OS is defined as time from first intratumoral injection to date of progression or death for any cause, whichever occurs first.
- PFS is defined as time from first intratumoral injection to date of progression or death for any cause, whichever occurs first.

- DOR is defined as time from first documentation of CR or PR for injected tumors as per Section 9.3.4 and overall, as determined by RECIST v.1.1.until disease progression or death for any cause, whichever occurs first.

Efficacy will be assessed in the population of subjects who receive three intratumoral administrations of Ad/PNP and any infusion of F-araAMP.

Descriptive statistics (number and percentage of subjects) will be used to summarize BOR, ORR, and durable response rate. 95% Clopper-Pearson confidence intervals will also be provided. OS, PFS, DOR, and TTR will be analyzed based on Kaplan-Meier methods; Kaplan-Meier curves will be plotted over time. The number and percentage of subjects identified to have had an event and those who were censored will be displayed. The median time to event and its corresponding 95% CI will also be produced. A listing of response for subjects will be provided.

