## 2 STUDY OBJECTIVES AND ENDPOINTS

Objectives	Endpoints

Primary:
 

To evaluate the safety of repeat administration of a dose level of Ad/PNP-F-araAMP that demonstrated anti-tumor activity in participants with advanced head and neck cancer in the completed Phase 1 study.

	

The primary endpoint is safety with repeat cycles of treatment. Safety measures include adverse events (AE) and laboratory parameters.

Secondary:
 

To evaluate the anti-tumor activity of repeat administration of Ad/PNP-F-araAMP, defined as participants who receive three intratumoral administrations of Ad/PNP and any infusion of F-araAMP.

	

Objective response rate (ORR), defined as the percentage of participants with a best overall response (BOR) of a complete response (CR) or a partial response (PR). BOR is the best response achieved during the up to 5 cycles of treatment, separately for injected tumors and overall as determined by RECIST v.1.1.

Durable response rate defined as a BOR of CR or PR, separately for injected tumors and overall as determined by RECIST v.1.1 persisting for at least 4 weeks.

Time to response (TTR) defined as time from first intratumoral injection to date of first response value of CR or PR, separately for injected tumors and overall as determined by RECIST v.1.1.

Overall survival (OS) defined as time from first intratumoral injection to date of death for any cause.

Progression free survival (PFS) defined as time from first intratumoral injection to date of progression or death for any cause, whichever occurs first, separately for injected tumors and overall as determined by RECIST v.1.1.

Duration of response (DOR) defined as time from first documentation of CR or PR until disease progression or death for any cause, whichever occurs first, separately for injected tumors and overall as determined by RECIST v.1.1 .

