#### 6.2.2.4 Overall Survival

Separately for injected tumors and overall (per RECIST v1.1), overall survival (OS) is defined as time from first intratumoral injection to date of death for any cause, and is calculated, in months, as:

(Date of death or censoring - date of first intratumoral injection + 1) / 30.4375.

Participants still alive as of the data cut-off date will be censored on the last known alive date from mortality status follow up. For participants that are lost to follow up, the last visit in the database or last contact date where the participant is documented to be alive will be used to estimate last known date alive.

OS will be analyzed based on the Kaplan-Meier methods described for PFS.

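### The SAP's overall survival analysis relies on mortality follow-up that the supplied protocol does not schedule, and progression sets the last planned contact, so late survival is likely to be overstated

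*Protocol*

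**What the plan says.** **Definition.** SAP section 2 has "Overall survival (OS) defined as time from first intratumoral injection to date of death for any cause". Protocol 12.6 differs: "OS is defined as time from first intratumoral injection to date of progression or death for any cause, whichever occurs first". The synopsis and section 10.3 of the protocol agree with 12.6, and that wording is the same as the protocol's definition of progression-free survival. SAP 1.1 nevertheless states that no protocol-specified analysis was changed.

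**Analysis and censoring.** SAP 6.2.2.4 says "OS will be analyzed based on the Kaplan-Meier methods described for PFS", which means a curve, a median and a 95% confidence interval. For the living it says "Participants still alive as of the data cut-off date will be censored on the last known alive date from mortality status follow up". For those lost to follow-up it falls back on "the last visit in the database or last contact date where the participant is documented to be alive". No cut-off date for survival is given. SAP 3.5 ties the final analysis to the last scheduled assessments.

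**Follow-up.** Protocol 4.2 says "No formal follow-up visits are planned following the end of the study period (Day 56 of the last treatment cycle"). The procedures table (Protocol 9.1, repeated in SAP Appendix 2) ends at Visit 9, and adverse-event recording stops on the same day (Protocol 7.5.1). The only later information is at the sponsor's option: "follow-up information from the investigator on tumor status in subjects who have stable disease (SD), PR, or CR" at the end of participation.

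**What sets the last cycle.** Under Protocol 4.2, progression of the injected tumor ends treatment before five cycles, and the participant then completes the Day 28 and Day 56 visits of that cycle.

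**The concern.** Kaplan-Meier assumes that a participant censored at a given time has the same later risk of death as those still under observation. Followed as written, this plan makes the last planned contact depend on when the injected tumor progressed. Someone who progresses in cycle 1 leaves view well before someone who completes five cycles. If progression worsens prognosis, the curve after the first exits rests increasingly on those who had not progressed.

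The optional later contact does not help. It covers tumor status, and only in participants without progression. If it yielded alive dates, it would lengthen follow-up for the better-prognosis group alone.

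At stake is a secondary result: an OS curve and median that could read better than the truth. Protocol 2.1 also describes prognosis after failed first-line chemotherapy in recurrent or metastatic squamous disease: it "is dismal, with median OS of < 6 months". Planned follow-up ends near that horizon.

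**Working it through.** **The plan's own figures.** The documents give no power, event count or precision for OS, so there is nothing of that kind to reproduce. The only power statement concerns the response rate (at least 3 of 10 responses, 10% against 40%). The exact binomial gives alpha 0.0702 and power 0.8327, matching the stated 7% and 83%. It does not bear on this point.

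**Step 1. Last planned contact.** Inputs are 28-day cycles (plus or minus 3 days) and a final visit at Day 56 (plus or minus 3) of the last cycle. For last cycle k, the nominal study day is 28 × (k − 1) + 56.

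| Last cycle | Study day | Months (÷ 30.4375) |
|---|---|---|
| 1 | 56 | 1.8 |
| 2 | 84 | 2.8 |
| 3 | 112 | 3.7 |
| 4 | 140 | 4.6 |
| 5 | 168 | 5.5 |

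The nominal gap between one cycle and five is 168 − 56 = 112 days, or 3.7 months. With every window at its upper limit, the five-cycle visit falls at 4 × 31 + 59 = 183 days, or 6.0 months. Dose delays (Protocol 4.3), or treatment resumed after a complete response has recurred (Protocol 4.2), can extend it further.

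**Step 2. Size of the bias under stated assumptions.** None of these inputs is in the documents. Half the participants stop early, with exits split equally between day 56 and day 84; half exit at day 168. Survival is exponential, with S1 for early stoppers and S2 for completers. At t = 5.4 months the Kaplan-Meier estimate tends to the product of three factors:

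- to day 56: 0.5·S1(56) + 0.5·S2(56)
- day 56 to 84: [0.25·S1(84) + 0.5·S2(84)] ÷ [0.25·S1(56) + 0.5·S2(56)]
- day 84 to t: S2(t) ÷ S2(84)

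The true value is 0.5·S1(t) + 0.5·S2(t).

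*Medians 3 and 9 months.* S1(56) = 0.6537, S2(56) = 0.8679, S1(84) = 0.5285, S2(84) = 0.8085, S1(t) = 0.2872, S2(t) = 0.6598. Kaplan-Meier: 0.7608 × 0.8979 × 0.8160 = 0.557. True: 0.1436 + 0.3299 = 0.473.

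*Medians 4 and 9 months.* S1(56) = 0.7270, S1(84) = 0.6199, S1(t) = 0.3923. Kaplan-Meier: 0.7974 × 0.9083 × 0.8160 = 0.591. True: 0.1962 + 0.3299 = 0.526.

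*Medians 6 and 6 months.* Both are 0.536, so there is no bias.

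Before day 56 nobody is censored by the schedule, so there is no bias. In the 3 and 9 month case the excess is about 1 point at 2.7 months (0.688 against 0.674), 4 points at 3.5 months (0.645 against 0.605) and 8 points at 5.4 months.

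**Step 3. A second model.** This simulation lets progression multiply the death hazard, detects progression at Day 14 of a cycle and censors at Day 56 of the last cycle. It assumes a true median OS of 5, 6 or 8 months and a median time to progression of 2 or 3.3 months. At day 167 the excess is about 3 to 8 points for hazard ratios of 2 to 8, and nil for a ratio of 1.

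**Step 4. Sampling error.** In the 3 and 9 month case the simulated standard deviation of the estimate at 5.4 months is about 19 points with 10 participants and 13 with 20. In the second model, with a true median of 6 months and 10 participants, about 3 to 4 deaths are observed and the median is reached in 26% to 46% of trials.

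**The case against.** Several points on the other side stand.

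- **Missing sources.** The SAP is also based on a case report form and a Protocol Clarification Letter (SAP section 1), neither of which was available. Either may contain a survival form, and Protocol 4.2 rules out formal visits rather than status checks. A reader might infer that mortality status is not collected at all. The documents support only that the supplied protocol does not schedule it.
- **Bias as a fact.** A reader might infer that survival is overstated. That requires progression to raise the risk of death, which is plausible but not established in the documents. Participants with no tumor left to inject also stop treatment. If they too were seen only to Day 56 of their last cycle, some good-prognosis participants would leave early and offset part of the bias, although Protocol 4.2 says complete responders continue to be followed during the study period.
- **An unobservable median.** A reader might infer that a median of 5.5 months or more can never be observed. The visit windows alone allow about 183 days, and interruptions allow longer.
- **Historical comparison.** None is planned for OS. The background figure concerns recurrent or metastatic squamous disease after first-line failure, whereas eligibility also covers salivary gland, nasopharyngeal and cutaneous tumors.
- **Definition.** Under the protocol's OS wording progression is itself an event, so early progressors are not censored at exit and the mechanism largely disappears. The point applies to the SAP's death-only OS.
- **Noise.** Random error at this sample size exceeds the bias. That limits what the curve can show, but it does not make the censoring non-informative.

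What remains is that the SAP names a data source absent from the supplied schedule, and that progression sets the planned end of observation.

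**Conclusion.** The point holds as a gap between the SAP and the supplied protocol. If no survival contact exists elsewhere, OS censoring is tied to progression, and late survival is likely to be overstated. In the two-group examples the excess at 5.4 months is about 8 points (3 and 9 months) and 6 to 7 points (4 and 9 months). It falls to nil with equal prognosis and is nil before day 56. These sizes rest on the assumed share of early stoppers, exit days and survival medians.

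At 10 to 20 participants sampling error is larger, and a median near 6 months would often not be reached, so an OS median would carry little information even without the bias. OS is secondary and no decision rule uses it. The primary safety conclusion and the response-rate rule are unaffected. The correction is still worth making, because it is cheap and removes the dependence.

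**What to change.** 1. Check the case report form and the clarification letter for a survival form. If one exists, cite it in SAP 6.2.2.4 and schedule the contact in the protocol.
2. Reconcile the OS definition between the protocol (synopsis, 10.3 and 12.6) and the SAP (2 and 6.2.2.4), and correct the statement in SAP 1.1 that nothing changed.
3. Otherwise, add one vital-status check by chart, telephone or public record for every treated participant, whatever the progression status. Use one common cut-off, such as the last participant's Day 56 visit, and censor those alive at that date. Censoring then depends on entry date rather than on progression.

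The cost is one query for at most 20 participants, plus protocol and consent wording.

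If this is not done, report the number of deaths and each participant's follow-up time descriptively instead of a Kaplan-Meier OS median, and state that censoring depends on progression. Protocol 12.6 specifies the curve and median, so this route needs a documented change and is not free of cost.

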4.3 Dose Modification

Based on monitoring of efficacy signal from subjects completing treatment, if no anti-tumor activity and no DLTs are observed, GeoVax may increase the dose of vector administered 5-fold from 2×10^{11} VP/dose to 1×10^{12} VP/dose, which was the high dose of vector used in the Phase 1 clinical trial. DLTs will be determined based on the incidence and intensity of AEs and SAEs assessed as being at least possibly related to Ad/PNP-F-araAMP and occurring up to 28 days after initiation of dosing on Cycle 1 Day 0. Formal approval from the Food and Drug Administration (FDA), IRB, and other regulatory offices as needed will be obtained prior to initiating an increase of vector dose. No serious toxicities were detected with this dose of vector (1×10^{12} VP/dose) in the earlier Phase 1 trial.

The total dose of F-araAMP per cycle is lower than that recommended to treat patients with hematological malignancies. Subjects who experience greater than Grade 2 neurotoxicity should be discontinued from treatment and followed for safety. The investigator may decrease the dose of F-araAMP to 15 mg/m^2 or delay administration based on evidence of high grade (CTCAE v5.0 Grade 3 or higher) hematologic or nonhematologic toxicity not recovered to baseline by day 1 of each subsequent cycle, with the exception of isolated lymphopenia, which will not require a dose reduction. Subjects who require further reduction in F-araAMP in the judgment of the investigator, based upon recurrent high grade AEs not resolved by day 1 of the subsequent cycle should be discontinued from treatment and followed for safety. Growth factor support is not to be used prophylactically in this study.

4.4 Expected Adverse Events

Local injection site reactions have been reported in clinical studies evaluating other non-replicating adenoviral vectors injected intratumorally. The Phase 1 study evaluated two dose levels of Ad/PNP (10^{11} VP/dose in Cohorts 1-3 and approximately 10^{12} VP/dose in Cohort 4) and 3 dose levels of F-araAMP (5, 15, and 25 mg/m^2 in Cohorts 1, 2, and 3, respectively and 25 mg/m^2 in Cohort 4). Among the 12 subjects in the study, the most frequently reported TEAEs were injection site pain (11 subjects, 91.7%) and fatigue (8 subjects, 66.7%). Injection site pain was reported in all but 1 subject receiving 10^{11} VP/dose + 15 mg/m^2 F-araAMP. The event was assessed as treatment-related in 10 subjects (83.3%); most reports were Grade 1 or 2 in severity. All Grade ≥ 3 events in our Phase I study were assessed as unrelated to study treatment, with the exception of 1 report of injection site pain as noted in this section. One subject receiving 10^{12} VP/dose experienced severe (Grade 3) injection site pain on Day 1 that was assessed as definitely related to Ad/PNP injection. The subject went on to complete the study receiving lidocaine injection prior to injection of Ad/PNP. Other injection site reactions included injection site discharge (4 subjects receiving either 10^{11} or 10^{12} VP/dose, 33.3%); injection site erythema, hemorrhage, and pruritus (2 subjects each receiving 10^{11} VP/dose, 16.7%), and injection site paresthesia (1 subject receiving 10^{12} VP/dose, 8.3%). All of these events were reported in only 1 subject within a cohort and all were assessed as Grade 1 or 2 in severity; most were reported as treatment-related.

F-araAMP is a purine analog used to treat patients with chronic lymphocytic leukemia (CLL). Besides being an anti-tumor agent against lymphoid malignancies, F-araAMP has immunosuppressant activity and is incorporated in preparatory regimens for allogeneic bone marrow transplantation.

When administered in cycles of the standard 25 mg/m^2 five-day course, F-araAMP induces myelosuppression (neutropenia, thrombocytopenia and anemia). Other commonly reported AEs include fever and chills, infection (including opportunistic infections), nausea and vomiting, malaise, fatigue, anorexia, and weakness. Life-threatening autoimmune hemolytic anemia has been reported in patients receiving F-araAMP. Objective weakness, agitation, confusion, visual disturbances, and coma have occurred in CLL patients treated with F-araAMP at the recommended dose. A high incidence of opportunistic infections, including *Pneumocystis jirovecii* pneumonia has been seen in CLL patients, especially those with a substantial history of steroid or alkylator use. Reactivations of latent viral infections such as VZV (herpes zoster), Epstein-Barr virus and JC virus (progressive multifocal leukoencephalopathy) have been reported in patients treated with F-araAMP. Additional information concerning drug related effects reported with F-araAMP are

described more fully in the package insert. It is unknown at this point whether any of these toxicities will be more or less pronounced when F-araAMP is given in conjunction with the Ad/PNP with repeat administration.

The toxicity attributable to intratumorally generated F-Ade with repeat injection is unknown. Based on results from a nonclinical study, systemic exposure to levels of F-Ade higher than expected in this study may cause myelosuppression and/or elevation in liver enzymes. Review of the safety and laboratory data from the Phase 1 clinical study showed that 2 of the 12 subjects experienced Grade ≥ 3 lymphopenia (neither were assessed as definitely related to study treatment) and no subject had elevation in liver enzymes. One of the two subjects with Grade ≥ 3 lymphopenia received 5 mg/m² F-araAMP and the other received 25 mg/m² F-araAMP daily for 3 days. Neither subject experienced a serious infection.

Two subjects experienced a serious infection. One subject developed a bacteremia related to a central intravenous line and another had a chronic wound over the tumor being injected. There were no reports of opportunistic infections.

4.4.1 Infection Prophylaxis

Although the dose regimen of F-araAMP is shorter than that used to treat hematological malignancy, there remains a potential risk for *Pneumocystis jiroveci* (PJP) infection with repeat cycles. Consequently, all subjects will receive prophylaxis antibiotic treatment, e.g., one double-strength trimethoprim (TMP)/sulfamethoxazole (SMX) (i.e., 160 TMP/800 SMX) three times a week. Prophylaxis will start prior to Day 1 of the first cycle and continue for 8 weeks following the last infusion of F-araAMP. Alternative acceptable prophylactic treatment may be used and should be recorded.

Additional prophylactic antibiotic therapy may be initiated in subjects with clinically relevant reduction in white blood cell counts per the investigator's assessment.

